8.2.2. Sensitivity Analyses

The following sensitivity analyses will be performed to assess the robustness of the results from the primary analysis:

- The primary analysis will be repeated on the PP Population.
- The CHM test stratified by the same pooled strata as in the primary analysis will be performed on the FAS population the missing data due to other reasons handled using the Last-Observation-Carried-Forward (LOCF) approach. Subjects who were rescued due to the protocol-specified worsening of uveitis or discontinued from the study due to lack of efficacy or adverse events prior to Month 5 will be treated as non-responders.
- Treatment policy strategy: The CHM test stratified by the same pooled strata as in the primary analysis will be performed on the FAS population regardless whether study eyes get rescued. The missing VH score will be imputed using multiple-imputation approach in the similar manner as described in Section 8.2.1.
- A generalized estimating equation (GEE) method will be used on observed cases up to Month 6 using identity link function. The GEE might be applied on the imputed data (via the same imputation approach as in primary analysis) if there are considerable large amount of missingness. The model will include pooled geographic region (US vs non-US), baseline VH score of the study eye (1.5+, 2+, '3+ or 4+'), treatment, visit, and treatment-by-visit as explanatory variables. An unstructured (UN) correlation structure will be used to model the correlation of the responses from subjects. For subjects rescued before Month 6, all VH scores of study eye collected after the start date of rescue therapy will be excluded from the analysis.
- If the UN correlation structure fails to converge, then an exchangeable (EXCH) correlation structure will be used to model the correlation. If the EXCH model fails to converge, then the independent model will be used.
- Multiple imputation with tipping point analysis will be performed to assess the impact of missing data on the primary analysis results. The following steps will be performed to generate different possible imputation scenarios:
 - Use Markov chain Monte Carlo (MCMC) to create monotone missingness first with VH score on the logarithm scale. Then obtain standard multiple imputations under MAR assumptions for missing VH scores using monotone regression on the logarithm scale. The missing data are filled in and 50 complete datasets are created. The seed that will be used in the SAS program is 135711.

- The imputed values for the treatment group will be added a different amount of 0.05, 0.10, 0.15, 0.20, and 0.25. The newly derived imputed values will be then converted into a eligible VH score based on the absolute distance.
- For each possible imputed scenario (associated with different added amounts), the primary analysis will be repeated and the p-values as well as the response rates will be obtained to determine whether the outcome under the scenario is positive or negative. The larger the added amount that required to reverse the conclusion of the primary analysis, the more robust the conclusion is considered to be.

No multiplicity adjustment will be made to these sensitivity analyses.

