3.3. Sample Size Planning

Assuming a 30% VH 0 response rate for DE-109 440 μ g group and a 12% response rate for the sham treatment group, 160 subjects (80 subjects per arm) is required to achieve 80% power to detect such a difference in response rate between the DE-109 440 μ g group and the sham treatment group using the Pearson's Chi-square test (two-sided, $\alpha = 0.05$). Including approximately 40 subjects in the dummy arm, a total of approximately 200 subjects with active NIU-PS will be randomized in a 2:2:1 ratio to DE-109 440 μ g, sham, and dummy arms. Because some subjects will contribute two study eyes to this study, the planned sample size of 80 subjects

in both the test (DE-109 440 $\mu g)$ and control (sham procedure) arms will achieve more than 80% power.

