5.4. Multiple Comparisons / Multiplicity

To control the overall Type I error rate associated with the multiple comparisons on the primary and the key secondary endpoints at the 0.05 level (two-sided), the following hierarchical testing strategy will be employed:

- A. Conduct the statistical testing for the primary comparison between DE-109 440 μg and Sham treatment arm on the primary endpoint (VH 0 response) at the significance level of 0.05 (two-sided)
- B. If the result of the primary comparison on the primary endpoint is positive (i.e., *p*-value < 0.05), then conduct the statistical testing for the primary comparison between DE-109 440 μg and Sham treatment arm on the following key secondary endpoints in a hierarchical fashion:
 - 1. Mean composite score at Month 5
 - 2. VH 0 response at Month 3
 - 3. Mean composite score at Month 3

The primary comparison on the $(i+1)^{th}$ key secondary endpoint will be performed inferentially ONLY IF the result of the primary comparison in the ith key secondary endpoint is positive, where i = 1 or 2.

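### The tipping-point analysis stops at a fixed shift of 0.25 on an unstated scale, so it can end before a reversal that exists, and non-reversal is then only a lower bound on robustness

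*SAP*

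**What the plan says.** SAP 8.2.2 lists a multiple-imputation tipping-point analysis among the sensitivity analyses of the primary endpoint. Missing VH scores are imputed under missing-at-random by MCMC and monotone regression on the logarithm scale, giving 50 datasets. The next step reads: "The imputed values for the treatment group will be added a different amount of 0.05, 0.10, 0.15, 0.20, and 0.25". After that, "The newly derived imputed values will be then converted into a eligible VH score based on the absolute distance". The primary analysis is repeated for each amount, with p-values and response rates reported. The reading rule is: "The larger the added amount that required to reverse the conclusion of the primary analysis, the more robust the conclusion is considered to be".

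The section gives no basis for 0.25, no instruction for the case where the conclusion still stands at 0.25, and no worst-case end point. It describes no back-transformation before the shift is added. SAP Table 2 lists the VH grades as 0, 0.5+, 1+, 1.5+, 2+, 3+ and 4+. Zero is therefore an eligible score, yet neither 8.2.1 nor 8.2.2 says how it is placed on a log scale. SAP 8.2.1 refers to SAS code in an Appendix C that is not in the text available here; the offset may be given there, and its absence is not counted as a fault.

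**The concern.** A tipping-point analysis is useful when it either finds the departure from missing-at-random that overturns the result or shows that no departure can. This one measures robustness by the size of the reversing shift, but searches only up to 0.25. If the reversal lies further out, the planned measure has no value, and the report would say that the conclusion was never reversed.

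A reader could take that as strong reassurance. How much reassurance it gives depends on how far 0.25 moves an imputed eye away from VH 0, and the text does not settle that. The analysis matters because it is the only planned one that deliberately worsens the imputed values for DE-109 relative to missing-at-random.

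**Working it through.** **Inputs from the documents.** Two-sided alpha 0.05 (SAP 5.4); design rates 30% and 12% with 80 subjects per arm (SAP 3.3); shifts 0.05 to 0.25 in the DE-109 arm only (SAP 8.2.2); VH grades (SAP Table 2).

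**Assumed, because the documents do not give them.** Log offset c from 0.01 to 1; missing rate in the test arm 5% to 30%; the Month 5 VH distribution; one eye per subject. P-values use a pooled two-proportion z-test and ignore strata, between-imputation variance and two-eye correlation, so they are approximate.

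**1. The plan's own figure.** SAP 3.3 says "160 subjects (80 subjects per arm) is required to achieve 80% power to" detect 30% against 12%.
n = [1.96·√(2·0.21·0.79) + 0.842·√(0.30·0.70 + 0.12·0.88)]² / 0.18² = 79.2, so 80 per arm. Power at 80 is 80.4%. The figure reproduces.

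**2. What 0.25 means on a log scale.** The log distance from VH 0 to VH 0.25, the midpoint between grades 0 and 0.5+, is log((0.25 + c)/c). If rounding is instead to the nearest grade on the log scale, it is ½·log((0.5 + c)/c).

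| Assumed offset c | To VH 0.25 | Nearest grade on log scale |
|---|---|---|
| 1 | 0.22 | 0.20 |
| 0.5 | 0.41 | 0.35 |
| 0.1 | 1.25 | 0.90 |
| 0.01 | 3.26 | 1.97 |

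Among these offsets, the largest planned shift moves an eye imputed at exactly VH 0 out of response only when c = 1.

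**3. How much stress 0.25 applies with offset 1.** Take log(VH+1) as normal with centre log(1 + m). The share of imputed eyes that respond is Φ((log 1.25 − shift − log(1 + m))/SD).

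| m | SD | No shift | +0.25 | Share of imputed responders removed |
|---|---|---|---|---|
| 0.5 | 0.35 | 30% | 11% | 64% |
| 0.5 | 0.50 | 36% | 19% | 46% |
| 1.0 | 0.35 | 9% | 2% | 78% |
| 1.0 | 0.50 | 17% | 7% | 57% |

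**4. A tipping point that the grid misses.** Take 26% against 12% with 80 eyes per arm, so 20.8 and 9.6 responders.
- Unshifted: pooled rate 0.19, SE = √(0.19·0.81·2/80) = 0.0620, z = 0.14/0.0620 = 2.26, p = 0.024.
- With 10% of test eyes missing, and imputed at the same 26% before any shift, the worst case has 20.8·0.9 = 18.72 responders (23.4%). Pooled rate 0.177, SE = 0.0603, z = 0.114/0.0603 = 1.89, p = 0.059. A reversal therefore exists.
- For the path to it, log(VH + c) is taken as normal, matched to an assumed grade distribution with 26% at VH 0, and rounded to the nearest grade on the log scale.

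| c | p at +0.25 | Shift at which p reaches 0.05 |
|---|---|---|
| 1 | 0.041 | 0.43 |
| 0.5 | 0.036 | 0.61 |
| 0.1 | 0.031 | 1.15 |
| 0.01 | 0.028 | 2.11 |

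For every offset the reversal lies beyond the last planned shift.

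**5. Where the grid does its job, or where there is nothing to find.**
- 25% against 12% (p = 0.034), 10% missing: tips at 0.17 (c = 1) or 0.24 (c = 0.5), inside the range, but at 0.46 (c = 0.1) or 0.84 (c = 0.01), outside it.
- 30% against 12% (p = 0.005), 20% missing: the worst case is 24·0.8 = 19.2 responders, and 24% against 12% gives p = 0.048. No shift confined to the test arm can tip it.
- The same rates with 25% missing: the worst case is 18 responders, p = 0.079. The tipping shift is 0.45, 0.65, 1.25 or 2.31 for c = 1, 0.5, 0.1 or 0.01, all beyond 0.25.

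**The case against.** **The planned grid is informative.** A conclusion that survives 0.25 has survived a real penalty: on the log(VH+1) model, about 46–78% of imputed DE-109 responders are removed. Response rates are reported for each scenario, and some marginal results reverse inside the range. This stands. A reader might infer that the analysis cannot show robustness at all, but the SAP does not support that. Non-reversal at 0.25 still gives a lower bound, and in some cases there is no tipping point to miss.

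**The most informative losses are already handled.** SAP 5.2.1 and 8.2.1 count protocol-specified worsening, and discontinuation for lack of efficacy or adverse events, as non-response. LOCF, treatment-policy, GEE and per-protocol analyses sit alongside. This limits how many eyes the shift can touch. It does not supply the missing stopping rule.

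**The log-scale shift is inferred.** The SAP never says outright on which scale the amount is added. If it is added after back-transformation, 0.25 is half the step from 0 to 0.5+, and under the assumed distributions the imputed response rate falls to about 7–12%. This stands as a caution, and it is itself a reason to state the scale.

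**Two stronger readings do not hold.** One is that shifts of 0.05 to 0.20 change nothing because scores are already rounded. In 8.2.2 the conversion to a grade comes after the shift. The other is that leaving sham unshifted is an error. Penalising only the active arm is a recognised design, and shifting sham as well is an optional extension.

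**Conclusion.** The point holds in a limited form. SAP 8.2.2 measures robustness by the reversing shift but stops at a fixed, unexplained 0.25, on a scale whose meaning depends on an offset that the available text does not give. Followed as written, it can stop before an existing reversal. In the 26% against 12% example, p at 0.25 is 0.028–0.041 while the worst case is 0.059. In such a case non-reversal should be reported as a lower bound and not as proof of robustness.

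The existence of that reversal depends on the assumed 10% missing rate, the imputed eyes responding at the observed rate before any shift, and the approximate test. Its position also depends on the assumed offset and VH distribution. The primary test is unaffected.

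**What to change.** In SAP 8.2.2:

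1. Add the shift on the VH scale, after back-transformation and before rounding to a grade. Alternatively keep it on the log scale and state the offset used for VH = 0 and that the shift is on that scale.
2. Replace the five fixed amounts with a rule: increase the shift until p reaches 0.05 or every imputed DE-109 eye is a non-responder.
3. Report the tipping value with the imputed response rate at that point, or state that no tipping point exists for a shift in the DE-109 arm.

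A two-way grid that also shifts sham may be added but is not needed to correct the plan. The cost is a few sentences of SAP text and a longer loop in the same program, settled before unmasking. No new data are needed.

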8.2.3. Analyses of Key Secondary Efficacy Endpoints

The following key secondary endpoints will be analyzed:

- Composite score at Month 5
- VH 0 response rate at Month 3
- Composite score at Month 3

All the key secondary endpoints will be analyzed using CMH test in the similar manner as the primary endpoint analysis. Study eyes with missing VH score at a given visit will be assigned with a score of 0 in the composite score system. For each composite score analysis, the raw mean score, Mantel-Haenszel weighted mean score, corresponding mean difference, its asymptotic 95% confidence interval, and p-values will be reported.

8.2.4. Analyses of Secondary Efficacy Endpoints

8.2.4.1. Analyses of Binary Secondary Endpoints

All binary secondary VH response endpoints and use of rescue therapy before Month 5 will be analyzed on the FAS using similar approach to the primary analysis.

For each of these binary endpoints, the frequency (n) and percent (%) of each treatment group will be reported. The Mantel-Haenszel weighted rates and rate difference and it 95% CI will also be reported.

BCVA binary endpoint defined in Section 8.1.9 will be descriptively summarized on observed cases for the Vision 20/40 or Worse Population. CST binary endpoint defined in Section 8.1.10 will be descriptively summarized on observed cases for the Macular Edema Population.

For each MMRM model, the denominator degrees of freedom for fixed effects will be estimated using the Kenward-Roger approximation (Kenward et al., 1997). An unstructured (UN) covariance matrix will be used to model the within-subject correlation due to study eyes and study visits. If the UN model fails to converge, then an autoregressive of order 1 (AR(1)) covariance matrix will be used to model the within-subject correlation due to study visits while study eye-related within-subject correlation structure remains unchanges. If the AR(1) model fails to converge, then the compound symmetry model will be used.

The following secondary endpoints will be analyzed using the analysis of covariance (ANCOVA) with missing data at Month 5 being imputed by the LOCF approach:

- Change from baseline in CST at Month 5 as measured by OCT
- Change from baseline in the NEI VFQ-25 composite score and subscales at Month 5

For the analysis of change from baseline in CST at Month 5, the ANCOVA model will include study eye, country (US or non-US), baseline systemic (oral) corticosteroid use status, and treatment as factors and baseline CST score as a covariate. Correlations of change from baseline in CST within a subject due to eyes will be modeled using UN structure.

For the analysis of changes from baseline in the NEI VFQ-25 composite score and subscales at Month 5, the ANCOVA model will include country (US or non-US), baseline systemic (oral) corticosteroid use status, baseline VH score of the study eye (1.5+, 2+, or '3+ or 4+') or the worse study eye (i.e., higher VH score) for subjects who enrolled both eyes, number of enrolled study eyes, and treatment as factors and baseline VFQ-25 score as a covariate.

For each of these continuous endpoints, the least squares (LS) mean change from baseline of each DE-109 group with its standard error will be reported. For each treatment comparison, the LS mean difference with the 95% CI will be reported.

8.3. Subgroup Analyses

The homogeneity of treatment effects among prospectively defined subgroups will be assessed via descriptive statistics of VH 0 response rate, including Mantel-Haenszel weighted rates and rate difference and it 95% CI, by the number of treated eyes for the following subgroups:

- Age (< 65 or \geq 65 years)
- Sex (males or females)
- Race (White or non-White)
- Country (US or non-US)
- Baseline VH score of the study eye (1.5+, 2+, or '3+ or 4+')
- Anatomic location of uveitis of study eye at baseline (intermediate, posterior, intermediate + posterior, or panuveitis)
- Intent-to-taper status at baseline (yes or no)
- Mean diurnal IOP at baseline ($< 25 \text{ or } \ge 25 \text{ mmHg}$)
- Baseline BCVA score of the study eye (≤ 70 letters or >70 letters)
- Baseline BCVA score of the study eye (≤ 65 letters or > 65 letters)
- Presence of macular edema in the study eye at baseline (yes [CST ≥ 300 microns] or no [CST < 300 microns])

Similarly, subgroup analyses will also be performed for the composite score. Other subgroup analyses may be performed as deemed necessary.

8.4. Exploratory Analyses

8.4.1. Analysis of combined total drug group

A total drug group consists of all FAS subjects who were randomized into either the DE-109 440 μ g arm or the DE-109 fixed dose (dummy) arm. The analysis of primary endpoint and key secondary endpoints will be applied on the total drug study group in comparison to the Sham arm.

8.4.2. Analysis of exploratory endpoints

For the analysis of BCVA-response endpoints based on Macular Edema population, response rate of each treatment, rate difference and its 95% confidence interval will be reported.

8.4.3. Bayesian analysis of the primary endpoint

8.4.3.1. Prior Data

The DE-109 clinical trial program includes Sakura 1 (32-007-S1) and Sakura 2 (32-007-S2), two randomized controlled trials in which subjects were randomized to the DE-109 study drug at one of three doses: 44 μ g, 440 μ g and 880 μ g. The inclusion/exclusion criteria in Sakura studies are very similar to those in LUMINA study, although inclusion criteria in Sakura studies were

slightly more liberal. The primary endpoint in the study (i.e., LUMINA study) will be analyzed using a Bayesian approach with Sakura data served as prior knowledge.

To ensure the similarity of data from subjects across trials, only Sakura studies' Intent-to-treat subjects who meet the additional following inclusion criteria will be included in the derivation of prior distribution:

- Having a BCVA ≥ 20 ETDRS letters and ≤ 75 ETDRS letters in the study eye(s) at the Day 1 visit.
- Subject being treated with systemic (oral) corticosteroids must have received a stable oral prednisone-equivalent dose between ≥15 mg/day and ≤40 mg/day at Day 1 visit.

The prior distribution representing the prior knowledge learned from a study will be derived based on the number of responders and number of subjects in the study population. If the previous study with N randomized subjects had n responders of the primary endpoint, the prior distribution for the response rate π will be

$$\pi \sim \text{Beta}(w \cdot n, w \cdot (N-n)),$$

where w represents the weight to compensate for possible variability from previous study and this study.

8.4.3.2. Bayesian Analysis

To assess the superiority of DE-109 440 μ g compared to Sham, a Bayesian analysis of the primary endpoint using Sakura studies data as prior knowledge will be employed. The prior distribution for the DE-109 440 μ g will be derived from Sakura 1 and Sakura 2 study, separately. For this analysis, the weight to account for possible variability across studies is chosen to be 40%, with other values will be used to assess the robustness of such choice. Prior distribution of Sham's response rate will be Beta (1, 1) as Sham has not been used as a comparator in previous studies. The posterior distribution of response rates will be calculated based on data collected from subjects who received DE-109 440 μ g and Sham in this study and the corresponding prior distribution, respectively.

The efficacy of DE-109 440 μ g is determined based on whether the posterior probability of DE-109 440 μ g superiority is met, that is

$$P(\pi_{440} - \pi_{sham} > 0 \mid Data) > 0.975$$

where π_{440} and π_{sham} are the response rate of the DE-109 440 µg and Sham arm, respectively.

To further assess the robustness of the Bayesian analysis, a sensitivity analysis will be performed where different weights (20%, 30%, 40%, 50%, and 60%) in the derivation of prior distribution will be used. Another sensitivity analysis with prior data including all Sakura studies' intent-to-treat subjects will also be performed.

9. SAFETY ANALYSES

9.1. Safety-Related Definitions

9.1.1. Adverse Event

An AE is defined as any untoward medical occurrence in a patient or clinical participant, temporally associated with the use of study intervention, whether or not related to the study intervention. An AE reported on the AE eCRF will be considered as *treatment-emergent* if the AE occurred on or after the treatment start date up to 120 days after treatment end date (or the last study visit). In other words, a reported event will not be counted as a treatment-emergent AE if it can be determined that the onset of the event occurred prior to the treatment start date or beyond 120 days after treatment end date. For tabulations of AEs during the Double-Masked analysis period or the Open-Label analysis period, only treatment-emergent AEs will be included. Note that events that occurred before the first administration of investigational product (IP) are considered medical history events and will be tabulated separately.

Each AE will be graded by the Clinical Investigator as Mild (aware or unaware of event, but easily tolerated), Moderate (discomfort enough to cause interference with usual activity), or Severe (incapacitating; unable to work or perform usual activity). AEs will also be rated by the Investigator as to their causality/relationship to the IP.

Each AE will be classified into a system organ class (SOC) and coded to a preferred term (PT) using Medical Dictionary for Regulatory Activities (MedDRA), version 23.1 published in 2020.

9.1.1.1. Ocular Adverse Event

An AE will be counted as an *ocular AE* if the Clinical Investigator selected "OD", "OS", or "OU" under 'Event Location' on the AE eCRF.

9.1.1.2. Adverse Drug Reaction

An AE will be counted as an adverse drug reaction (ADR) if

- the AE was considered *study medication*-related, i.e., the Clinical Investigator answered 'Related' to the AE eCRF question "Relationship to Study Drug", **OR**
- the AE was considered injection procedure-related, i.e., the Clinical Investigator answered 'Related' to the AE eCRF question "Relationship to Study Drug injection procedure"

9.1.1.3. Serious Adverse Event

An AE will be counted as a *serious adverse event* (SAE) if the Clinical Investigator selected "Yes" to the question 'Is the adverse event serious?' on the AE eCRF. Any AE is considered a SAE if it fulfills one or more of the following criteria:

- Death (i.e., the AE caused or led to death)
- Life threatening (i.e., immediately life-threatening)
- It required or prolonged inpatient hospitalization.

- It resulted in a persistent or significant disability/incapacity (i.e., the AE resulted in a substantial disruption of the subject's ability to carry out normal life functions).
- It resulted in a congenital anomaly/birth defect in the offspring of a study subject who was exposed to study therapy prior to conception or during pregnancy.
- It is a medically significant event(s), which may include "sight-threatening events," that may not meet any of the above serious criteria but may jeopardize the subject or require medical or surgical intervention to prevent one of the outcomes listed above.

